### Incidence of Hospitalization to Treat Seizures

Hospitalization data will be captured in the CRF and will be used to calculate incidence.

The number and percentage of subjects who utilized medical center care to treat a seizure will be presented by treatment group for the T+M period. Statistical comparisons of the differences between treatment and placebo groups will be based on Cochran-Mantel-Haenszel test stratified by age group.

### Incidence of Status Epilepticus

The incidence of status epilepticus will be evaluated based on cases captured as such with treatment at hospitals or other treatment centers, those entered as adverse events (including SAEs) into the safety database, and also as convulsive seizures lasting longer than 10 min from the seizure diary. A single seizure meeting more than one of these criteria will be counted once. According to the ILAE, seizures of this duration are to be considered SE.

The number and percentage of subjects with status epilepticus recorded as an AE will be presented by treatment group for the baseline and the T+M period per 28 days.

In addition, the number and percentage of subjects who experience at least one convulsive seizure with duration > 10 min will be reported for the baseline and T+M period.

All seizures recorded in the AE database as status epilepticus should also be included in the seizure diary. An edit check will be performed to identify the overlap between seizures identified as AE of SE and seizures entered into the diary as seizures > 10 min. The "calculated" number and percentage of subjects experiencing SE will be presented by treatment group, defined as individuals who experience either an AE of SE, medical treatment for SE, or a seizure lasting longer than 10 min. Each subject will be represented once regardless of incidence.

A statistical comparison of the differences between the ZX008 0.8 mg/kg/day and placebo groups will be based on a logistic regression model with a categorical response (experienced at least one SE as an AE or a seizure > 10 minutes during T+M, yes or no) as a function of treatment group (active or placebo), age group (< 6 years, ≥ 6 years), and a categorical baseline variable (experienced at least one SE as an AE or a seizure > 10 minutes during Baseline, yes or no). An analogous model will be used to compare the ZX008 0.2 mg/kg/day group to placebo.

The number of incidences of status epilepticus will be cross-tabulated against the incidences of rescue medication uses (Yes/No). Cochran–Mantel–Haenszel test (CMH) test will be used to test the general association between incidences of SE and rescue medication uses.

This document is confidential.

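### Study 2 SAP: the only between-arm test of status epilepticus omits medical treatment for SE, a source that the section's own definition and calculated count include

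*SAP*

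**What the plan says.** All of this stands under Incidence of Status Epilepticus in Section 8.2.2 of the Study 2 SAP.

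- **Opening definition.** SE is evaluated from three sources. The first is "cases captured as such with treatment at hospitals or other treatment centers". The second is AEs and SAEs of SE held in the safety database. The third is the diary: "also as convulsive seizures lasting longer than 10 min from the seizure diary". If one seizure meets more than one criterion, it counts once.
- **Single-source counts.** Subjects with an AE of SE are reported, and so is "the number and percentage of subjects who experience at least one convulsive seizure with duration > 10 min". Both are given for Baseline and T+M.
- **Calculated count.** This is a count of subjects, "defined as individuals who experience either an AE of SE, medical treatment for SE, or a seizure lasting longer than 10 min", each subject once.
- **Test.** Each dose is compared with placebo by logistic regression. The response is "experienced at least one SE as an AE or a seizure > 10 minutes during T+M, yes or no". The covariates are age group and a baseline yes/no variable built from the same two sources.

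The section's other test, a Cochran-Mantel-Haenszel test, relates SE to rescue medication use and does not compare arms.

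Sections 2.2 and 4 list SE incidence as an additional secondary endpoint, and Section 2.2 frames it as a superiority objective for each dose.

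**The concern.** The section sets a three-source definition, reports a count that uses it, and then tests a two-source event. Nothing in the SAP explains why medical treatment for SE is left out of the model.

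The odds ratio and p-value for a stated superiority objective would then rest on a different set of events from the one that the section defines. A reader of the report would naturally attach them to the calculated count. SE is likely to affect only a minority of about 40 subjects per arm, so even one or two reclassified children could matter to a nominal p-value.

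**Working it through.** The SAP states no SE rate, power or sample size for this endpoint, so there is no figure to reproduce. The main check is a comparison of the text.

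**Step 1: the definitions side by side**

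| Place | AE of SE | Medical treatment for SE | Seizure >10 min |
|---|---|---|---|
| Opening definition | yes | yes | yes, convulsive |
| AE-only count | yes | no | no |
| >10 min count | no | no | yes, convulsive |
| Calculated count | yes | yes | yes, adjective absent |
| Logistic response, T+M | yes | **no** | yes, adjective absent |
| Baseline covariate | yes | **no** | yes, adjective absent |
| Study 1 SAP, Section 6.3.3.7, calculated count, compared by Fisher's exact test | yes | yes | yes, adjective absent |

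**Step 2: who is counted but not tested**

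Let A be subjects with an AE of SE, M those with medical treatment for SE, and D those with a seizure >10 min.

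- Counted: A ∪ M ∪ D.
- Tested: A ∪ D.
- Difference: those in M who are in neither A nor D.

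A prolonged non-convulsive seizure is handled alike in the calculated count and the model, because neither uses the adjective. It does not contribute to this difference.

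**Step 3: is the difference empty by construction?**

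No. The planned edit check compares AEs of SE with diary seizures >10 min, that is, A with D. No check links M to either. Medical-centre care is a separate CRF source, described under Incidence of Hospitalization to Treat Seizures.

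**Step 4: how much one subject could matter (illustration only)**

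Inputs: 40 per arm (Section 2.5); event counts assumed. The test is the two-sided Fisher's exact test. With m events in total, P(x) = C(40,x)·C(40,m−x)/C(80,m), and p is the sum of P(x) over tables no more probable than the observed one.

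| Two-source events, placebo vs active | p | Change | p after |
|---|---|---|---|
| 12 vs 4 | 0.048 | one added in active: 12 vs 5 | 0.099 |
| 12 vs 4 | 0.048 | one added in placebo: 13 vs 4 | 0.027 |
| 10 vs 3 | 0.066 | one added in placebo: 11 vs 3 | 0.037 |
| 14 vs 6 | 0.069 | one added in placebo: 15 vs 6 | 0.041 |

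**Step 5: power if a share f of event subjects is missed equally in both arms (illustration only)**

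The rates and f are assumed. The rates become p(1−f). Power is the binomial probability, enumerated at 40 per arm, that the unstratified Mantel-Haenszel chi-square exceeds 3.84.

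| True rates, placebo vs active | f = 0 | 5% | 10% | 20% | 30% |
|---|---|---|---|---|---|
| 35% vs 10% | 0.79 | 0.77 | 0.74 | 0.68 | 0.61 |
| 40% vs 15% | 0.72 | 0.69 | 0.66 | 0.60 | 0.53 |

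Neither calculation is the planned logistic model, which adjusts for age group and baseline SE. They show sensitivity and do not predict a result.

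**The case against.** **Few subjects should be affected.** Section 10.3 defines an AE broadly and collects AEs from consent to Visit 13. SE treated at a centre should usually appear as an AE, and the SAP expects AEs of SE to be in the diary as well. A child with neither record would usually reflect a recording lapse. This stands as a limit on size, but the plan has no check that makes the number zero.

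**The tested events are still reported.** If a seizure means a convulsive seizure, the response is the union of the AE-only and >10 min counts. This stands too. A reader might infer that the test matches nothing that is reported; the document does not support that. The mismatch is with the opening definition and the calculated count.

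**Two sources may have been chosen so that response and baseline match.** Medical-centre care is presented only for T+M, and the schedule in Table 4 has no hospitalization row, so capture during Baseline is not shown. This could explain the covariate, but the SAP gives no such reason. It also would not require dropping the source from the T+M response.

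**The convulsive wording is probably shorthand.** The next part of the section, on seizure duration, also opens with the adjective and then drops it. A reader might take the switch as a second gap between counted and tested events. It is not one, because both use the same wording.

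**The consequence is limited.** SE lies outside the six-step hierarchy of Section 6.3, and medical-centre care for seizures has its own between-arm test. Both points hold.

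A reader might also suppose that the omitted source holds the better-verified cases, or that a known amount of power is lost. The SAP says nothing about the relative reliability of the sources, and it gives neither SE rates nor overlap.

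**Conclusion.** The point holds as an internal inconsistency in the Study 2 SAP. As written, SE is defined and counted from three sources and tested on two. The subjects affected are those known only through medical treatment for SE. Nothing in the document reconciles the two, and the Study 1 SAP tested the three-source count.

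The size is unknown and may be zero. If there are such subjects, the direction of the effect depends on their arms, so no direction of bias can be claimed. The p-value and power figures rest wholly on assumed counts, rates and missed shares. The primary conclusion, the six-step hierarchy and overall Type 1 error control are unaffected. The convulsive wording is a secondary matter of consistency.

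The change is worth making because it is cheap and the endpoint supports a stated superiority objective for each dose.

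**What to change.** Before Study 2 is unblinded, state one definition under Incidence of Status Epilepticus, using the section's own three sources: an AE of SE, or medical-centre treatment for SE, or a diary convulsive seizure longer than 10 minutes, each subject once.

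- Use it for both the calculated count and the logistic response in T+M.
- Use it for the baseline covariate as well if medical-treatment data are available for Baseline. If not, keep the two-source covariate and say so in the SAP.
- Write convulsive wherever the diary criterion appears, or state that the shorter wording carries that meaning.

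The cost is a few lines of SAP text and one derived variable for T+M, plus a check of whether medical treatment for SE was recorded during Baseline. The section already names all three sources for evaluating SE.

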### Duration of Prolonged Seizures

Duration of convulsive seizures at baseline and on treatment will be presented by treatment group using categories as <2 min, 2-10 min and >10 min.

To obtain a baseline probability distribution for the 3 categories, we will proceed as follows: For each subject, we will calculate the percentage of their total number of baseline seizures that is in each category. (For example, if the subject had 5 seizures, with 2 in the first category and 3 in the last category, their percentage distribution would be 40%, 0%, and 60% in the <2, 2-10, and >10 categories. We can calculate similar numbers for the next subject, and so on.) We will then average these over all subjects to obtain the % of subjects' seizures that were <2 min in duration, the % between 2-10 min in duration, and the % >10 min in duration. These 3 percentages should total 100%. Thus we will obtain a distribution of seizure duration for baseline.

Using the seizure duration data obtained for the T+M period, we will proceed similarly, to obtain a distribution for the T+M period.

It is expected that treatment with ZX008 will result in shorter duration of seizures (as well as fewer seizures) during T+M compared to placebo, i.e., the probability of longer seizures (> 10 min) will be higher for the placebo group than for the ZX008 arms. This may be assessed by comparing the probability of a >10 min seizure during T+M to the same during baseline, for a treatment group, to the same for the Placebo group. It is expected that the ZX008 group will have greater odds of a reduction in proportion of seizures >10 min than the Placebo group. However, treatment with ZX008 may result in fewer seizures overall yet the duration of residual seizures may not be shorter. Should the primary or key secondary endpoints be positive for a given dose(s), but the duration of seizures not be shortened per above, exploratory evaluations may be undertaken to better understand the effect.

### Clinical Global Impression – Improvement Rating, as assessed by the Parent/Caregiver

The parent/caregiver and the investigator will rate their global impression of the subject's condition at each clinic visit after randomization: end of Titration period (Visit 6), Maintenance period (Visit 8 and 10), and at End of study (Visit 12).

The CGI-I scale measures the change in the subject's clinical status from a specific point in time, i.e., the Baseline Period. The CGI-I rating scale permits a global evaluation of the subject's improvement over time. The severity of a patient's condition is rated on a 7-point scale ranging from 1 (very much improved) to 7 (very much worse) as follows:

- 1=very much improved
- 2=much improved
- 3=minimally improved
- 4=no change
- 5=minimally worse
- 6=much worse
- 7=very much worse

The mean (SD) CGI-I score, and the number and percentage of subjects who showed improvement (i.e., had a score of 3 or lower), and the number and percentage who did not improve (i.e., had a score of 4 or higher) will be presented for each for each treatment group at each assessment timepoint. Each assessment time point will also include a comparison between each active treatment and the placebo group using the Cochran-Mantel-Haenszel test stratified by age group, and a frequency distribution of the

This document is confidential.

**Statistical Analysis Plan**

Sponsor: Zogenix International Limited; Protocol No.: ZX008 Study 2 (ZX008-1501 and ZX008-1502)

number and percentage of subjects in each category in the scale. A histogram of the frequency distribution will be presented.

The number and percentage of subjects who were much or very much improvement (i.e., had a score of 2 or lower), and the number and percentage who were minimally improved or did not improve (i.e., had a score of 3 or higher) will also be presented for each for each treatment group at each assessment timepoint as an exploratory analysis.

Individual subject CGI data will be listed.

**Clinical Global Impression – Improvement Rating, as assessed by the Principal Investigator**

CGI-I score data assessed by the principal investigator will be summarized and analyzed using the same methods used for CGI-I score data recorded by parent/caregiver as above.

**Quality of Life in Childhood Epilepsy (QOLCE) Scale**

The parent/caregiver will complete this questionnaire for the QOLCE. This assessment looks at how epilepsy affects day-to-day functioning of their child in various life areas, including physical activities, well-being, cognition, social activities, behavior and general health, at baseline period (Visit 3), at Maintenance period (Visit 8) and at End of study/ET (Visit 12). There is also one question on overall quality of life, administered as part of the QOLCE.

The QOLCE scores items with a possible 5 point response. [Not including “6”, “Not Applicable.”] To calculate subscale scores, the 5 point item scores will first be reverse coded as necessary so that scores of 5 represent the best possible response and 1 represents the worst possible response. Item scores will then be transformed to a 0-100 scale as follows: 1-0, 2-25, 3-50, 4-75, 5-100. After transformation, a score for each subject for each subscale is calculated by averaging that subject’s responses to each item in the subscale. [A value of 0 represents the lowest or poorest score and 100 reflects the highest level of functioning.] The 16 subscale scores per subject are then averaged to obtain an overall quality of life score for each subject. The mean and SD across all subjects are then calculated for each subscale, including the overall quality of life score. The higher the subscale and overall quality of life scores, the better the response.

Table 2: Subscale of QOLCE:

Domain	Subscale	Item
Section 3: Physical	Physical Restrictions	3.1 a-j
Section 3: Physical	Energy/Fatigue	3.2 a,b
Section 4: Well-being	Depression	4.1 a,d,e,l
Section 4: Well-being	Anxiety	4.1 b,g,j,n,o,p
Section 4: Well-being	Control/helplessness	4.1 c,f,h,i
Section 4: Well-being	Self-esteem	4.1 k,m,q,r,s
Section 5: Cognition	Attention/Concentration	5.1 a,d,e,f,g
Section 5: Cognition	Memory	5.1 j,k,l,m,n,o
Section 5: Cognition	Language	5.1 p,q,r,s,t,u,v,w
Section 5: Cognition	Other Cognitive	5.1 b,c,h
Section 6: Social Activities	Social Interactions	6.1 c,f,h
Section 6: Social Activities	Social Activities	6.1 a, e, 6.2

This document is confidential.

**Statistical Analysis Plan**

Sponsor: Zogenix International Limited; Protocol No.: ZX008 Study 2 (ZX008-1501 and ZX008-1502)

Section 6: Social Activities	Stigma Item	6.1 i
Section 7: Behavior	Behavior	7.1 a, c, f, g, h, i, j, k, l, m, o, q, r, s, t
Section 8: General Health	General Health Item	8.1
Section 2 (USA Version) or Section 9 (Australia Version)	Quality of Life Item	2.1 or 9.1
Overall Quality of Life *		Average of 16 subscale scores*

\*An Overall Quality of Life Score can be computed by adding each subscale score for each individual and then dividing by 16.

For each treatment group at Baseline and End of Study/ET, the mean (SD) score will be presented for each QOLCE subscale and for the overall quality of life score.

In addition, the change from baseline in the overall QOLCE will be calculated for each subject by subtracting the baseline overall score from the overall score measured at End of Study/ET. The change from baseline for each treatment group will be summarized by the mean (SD) and treatment groups will be compared using pairwise Wilcoxon tests.

Individual subject data for the domains will be listed.

**Quality of Life of the Parent/Caregiver using EQ-5D-5L Scale**

The impact on the quality of life of the parent/caregiver responsible for a patient with DS will be assessed at Baseline (Visit 3) and at End of study (Visit 12) using the EQ-5D-5L. The responsible parent/caregiver was permitted to opt out of completing the EQ-5D-5L.

The EQ-5D-5L health questionnaire is a health-related quality of life instrument with 5 dimensions: mobility, self-care, usual activities, pain/discomfort, and anxiety/depression. Each dimension has 5 possible levels: no problems, slight problems, moderate problems, severe problems and extreme problems.

The summary of results will follow the EQ-5D-5L guideline results presentation. For the "Health Profiles" descriptive system summary results will show the number, and proportion (%) of subjects in each Item score (No Problems, Slight Problems, Moderate Problem, Severe Problem, Extreme Problems) by treatment at baseline and at the end of study. In addition, the item scores will be classified into two categories as "No Problems" and "Problems," the latter comprised of slight, moderate, severe and extreme problems. Summary results will show number of patients and proportion (%) with "No Problems" and with "Problems" by treatment at baseline and at end of study.

For the VAS measure of overall self-rated health status, descriptive statistics summary results will be presented for the VAS score showing number of subjects, mean, standard deviation, median, and range by each treatment at baseline and end of study time points.

The change from baseline in VAS will be calculated by subtracting the VAS score at baseline from the VAS score obtained at End of Study/ET. The change in VAS will be summarized using descriptive statistics, and treatment groups will be compared using pairwise Wilcoxon tests.

The quality of life of parent/caregiver individual data will be listed using EQ-5D-5L scale.

This document is confidential.

## Statistical Analysis Plan

Sponsor: Zogenix International Limited; Protocol No.: ZX008 Study 2 (ZX008-1501 and ZX008-1502)

### Parent/Caregiver Assessment using HADS Scale

The HADS is a tool commonly used to determine the levels of anxiety and depression that a person is experiencing and is administered to the primary parent/caregiver to assess these symptoms longitudinally during the study. The responsible parent/caregiver was permitted to opt out of the HADS. The HADS is a 14-item scale that generates ordinal data for two dimensions: 1) Anxiety and 2) Depression. Seven of the items relate to anxiety and 7 relate to depression.

Each item has 4 possible answers rated 0-3. All answers to the items for a dimension with their respective rating are added resulting in a range for each dimension from 0-21. Scores for the entire scale (emotional distress) range from 0 to 42, with higher scores indicating more distress.

Summary descriptive statistics including the mean and SD will be generated separately for the Anxiety and Depression dimensions at both Baseline and at End of Study/ET. In addition, each subject will be categorized at each time point based on the score cut-offs below which were validated on adult patients in a treatment setting.

Score	Category
0-7	Normal
8-10	Borderline abnormal
11-21	Abnormal

Summary statistics will include number and proportion (%) of subjects in each of the categories above at each study visit.

In addition, the total score for Anxiety and Depression will be generated. Descriptive statistics summaries including mean, median, standard deviation, median and range will be summarized for each treatment at Baseline and End of Study/ET.

The change from baseline for each subject will be calculated by subtracting the total Anxiety and Depression score measured at Baseline from the analogous score measured at End of Study/ET. The change from baseline will be summarized by descriptive statistics and the difference between treatment groups will be assessed using pairwise Wilcoxon tests.

The individual item outcomes will be presented in the subject data listing.

### Pediatric Quality of Life Inventory (PedsQL 4.0 Generic Core) Scale

The PedsQL 4.0 is a quality of life scale that measures four functional areas (physical, emotional, social, and school functioning). The scale is available in age-appropriate instruments with child self-report and parent proxy-report formats. In this study, the age appropriate categories for the administration of the instrument were ages 2-4, 5-7, 8-12 and 13-18 years, and the Parent Reports were used.

There are 8 items for Physical Functioning, and 5 questions each for Emotional, Social, and School Functioning. Each of the responses to the 23 items is initially scored on a 5 point Likert scale from 0 (Never) to 4 (Almost always). Scores will be linearly transformed to a scale of 0 to 100, where 0=100, 1=75, 2=50, 3=25 and 4=0, and higher scores mean better health related quality of life. If more than 50% of the items in the scale are missing, the scale scores should not be computed. A mean score is calculated as the sum of the items over the number of items answered. If some of the answers on a scale are missing but 50% or more of the items in the scale are completed, then impute the mean of the

This document is confidential.

